### **Hematopoietic Growth Factors and Blood Products**

Erythropoietin, darbepoetin alfa, romiplostim and/or hematopoietic colony-stimulating factors for treatment of cytopenias should be administered according to institutional guidelines. Transfusion thresholds for blood product support will be in accordance with institutional guidelines.

## **12.0 CRITERIA FOR THERAPEUTIC RESPONSE/OUTCOME ASSESSMENT**

### **Antitumor Effect – Solid Tumors**

Response and progression will be evaluated in this study using the new international criteria proposed by the revised Response Evaluation Criteria in Solid Tumors (RECIST) guideline (version 1.1) [22]. Changes in the largest diameter (unidimensional measurement) of the tumor lesions and the shortest diameter in the case of malignant lymph nodes are used in the RECIST criteria.

### **12.1 Definitions**

Evaluable for toxicity. All patients will be evaluable for toxicity from the time of their first treatment on study.

Evaluable for objective response. Only those patients who have measurable disease present at baseline, have received at least one cycle of therapy, and have had their disease re-evaluated will be considered evaluable for response. These patients will have their response classified according to the definitions stated below. (Note: Patients who exhibit objective disease progression prior to the end of cycle 1 will also be considered evaluable.)

Evaluable Non-Target Disease Response. Patients who have lesions present at baseline that are evaluable but do not meet the definitions of measurable disease, have received at least one cycle of therapy, and have had their disease reevaluated will be considered evaluable for non-target disease. The response assessment is based on the presence, absence, or unequivocal progression of the lesions.

### **12.2 Disease Parameters**

Measurable disease. Measurable lesions are defined as those that can be accurately measured in at least one dimension (longest diameter to be recorded) as >20 mm by chest x-ray, as >10 mm with CT scan, or >10 mm with calipers by clinical exam. All tumor measurements must be recorded in millimeters (or decimal fractions of centimeters).

Note: Tumor lesions that are situated in a previously irradiated area will not be considered measurable unless progression is documented or a biopsy is obtained to confirm persistence at least 90 days following completion of radiation therapy.

Malignant lymph nodes. To be considered pathologically enlarged and measurable, a lymph node must be >15 mm in short axis when assessed by CT scan (CT scan slice thickness recommended to be no greater than 5 mm). At baseline and in follow-up, only the short axis will be measured and followed.

Non-measurable disease. All other lesions (or sites of disease), including small lesions (longest diameter <10 mm or pathological lymph nodes with  $\geq 10$  to <15 mm short axis), are considered non-measurable disease. Bone lesions, leptomeningeal disease, ascites, pleural/pericardial effusions, lymphangitis cutis/pulmonitis, inflammatory breast disease, and abdominal masses (not followed by CT or MRI), are considered as non-measurable.

Note: Cystic lesions that meet the criteria for radiographically defined simple cysts should not be considered as malignant lesions (neither measurable nor non-measurable) since they are, by definition, simple cysts.

‘Cystic lesions’ thought to represent cystic metastases can be considered as measurable lesions, if they meet the definition of measurability described above. However, if non-cystic lesions are present in the same patient, these are preferred for selection as target lesions.

Target lesions. All measurable lesions up to a maximum of 2 lesions per organ and 5 lesions in total, representative of all involved organs, should be identified as target lesions and recorded and measured at baseline. Target lesions should be selected on the basis of their size (lesions with the longest diameter), be representative of all involved organs, but in addition should be those that lend themselves to reproducible repeated measurements. It may be the case that, on occasion, the largest lesion does not lend itself to reproducible measurement in which circumstance the next largest lesion which can be measured reproducibly should be selected. A sum of the diameters (longest for non-nodal lesions, short axis for nodal lesions) for all target lesions will be calculated and reported as the baseline sum diameters. If lymph nodes are to be included in the sum, then only the short axis is added into the sum. The baseline sum diameters will be used as reference to further characterize any objective tumor regression in the measurable dimension of the disease.

Non-target lesions. All other lesions (or sites of disease) including any measurable lesions over and above the 5 target lesions should be identified as non-target lesions and should also be recorded at baseline. Measurements of these lesions are not required, but the presence, absence, or in rare cases unequivocal progression of each should be noted throughout follow-up.

## 12.3 Methods for Evaluation of Measurable Disease

All measurements should be taken and recorded in metric notation using a ruler or calipers. All baseline evaluations should be performed as closely as possible to the beginning of treatment and never more than 4 weeks before the beginning of the treatment. The same method of assessment and the same technique should be used to characterize each identified and reported lesion at baseline and during followup. Imaging-based evaluation is preferred to evaluation by clinical examination unless the lesion(s) being followed cannot be imaged but are assessable by clinical exam.

**Clinical lesions:** Clinical lesions will only be considered measurable when they are superficial (e.g., skin nodules and palpable lymph nodes) and  $\geq 10$  mm diameter as assessed using calipers (e.g., skin nodules). In the case of skin lesions, documentation by color photography, including a ruler to estimate the size of the lesion, is recommended.

**Chest x-ray:** Lesions on chest x-ray are acceptable as measurable lesions when they are clearly defined and surrounded by aerated lung. However, CT is preferable.

**Conventional CT and MRI:** This guideline has defined measurability of lesions on CT scan based on the assumption that CT slice thickness is 5 mm or less. If CT scans have slice thickness greater than 5 mm, the minimum size for a measurable lesion should be twice the slice thickness. MRI is also acceptable in certain situations (e.g. for body scans), but NOT lung.

Use of MRI remains a complex issue. MRI has excellent contrast, spatial, and temporal resolution; however, there are many image acquisition variables involved in MRI, which greatly impact image quality, lesion conspicuity, and measurement. Furthermore, the availability of MRI is variable globally. As with CT, if an MRI is performed, the technical specifications of the scanning sequences used should be optimized for the evaluation of the type and site of disease. Furthermore, as with CT, the modality used at follow-up should be the same as was used at baseline and the lesions should be measured/assessed on the same pulse sequence. It is beyond the scope of the RECIST guidelines to prescribe specific MRI pulse sequence parameters for all scanners, body parts, and diseases. Ideally, the same type of scanner should be used and the image acquisition protocol should be followed as closely as possible to prior scans. Body scans should be performed with breath-hold scanning techniques, if possible.

**PET-CT:** At present, the low dose or attenuation correction CT portion of a combined PET-CT is not always of optimal diagnostic CT quality for use with RECIST measurements. PET-CT scans are not always done with oral and IV contrast. In addition, the PET portion of the CT introduces additional data which may bias an investigator if it is not routinely or serially performed. For these reasons, the GOG will not allow PET-CT use for RECIST 1.1 response criteria.

**Ultrasound:** Ultrasound is not useful in assessment of lesion size and should not be used as a method of measurement. Ultrasound examinations cannot be reproduced in their entirety for independent review at a later date and, because they are operator dependent, it cannot be guaranteed that the same technique and measurements will be taken from one

assessment to the next. If new lesions are identified by ultrasound in the course of the study, confirmation by CT or MRIs advised. If there is concern about radiation exposure at CT, MRI may be used instead of CT in selected instances.

**Endoscopy, Laparoscopy:** The utilization of these techniques for objective tumor evaluation is not advised. However, such techniques may be useful to confirm complete pathological response when biopsies are obtained or to determine relapse in trials where recurrence following complete response (CR) or surgical resection is an endpoint.

**CA125 (Ovarian, fallopian tube and primary peritoneal cancer trials):** CA125 alone cannot be used to assess response. If CA125 is initially above the upper normal limit, it must normalize for a patient to be considered in complete clinical response. Specific guidelines for CA-125 response (in recurrent ovarian cancer) have been published (23) In addition; the Gynecologic Cancer Intergroup has developed CA-125 progression criteria which are to be integrated with objective tumor assessment for use in first-line trials in ovarian cancer (24).

**Cytology, Histology:** These techniques can be used to differentiate between partial responses (PR) and complete responses (CR) in rare cases (e.g., residual lesions in tumor types, such as germ cell tumors, where known residual benign tumors can remain).

The cytological confirmation of the neoplastic origin of any effusion that appears or worsens during treatment when the measurable tumor has met criteria for response or stable disease is mandatory to differentiate between response or stable disease (an effusion may be a side effect of the treatment) and progressive disease.

**FDG-PET:** While FDG-PET response assessments need additional study, it is sometimes reasonable to incorporate the use of FDG-PET scanning to complement CT scanning in assessment of progression (particularly possible 'new' disease). New lesions on the basis of FDG-PET imaging can be identified according to the following algorithm:

- a. Negative FDG-PET at baseline, with a positive FDG-PET at follow-up is a sign of PD based on a new lesion.
- b. No FDG-PET at baseline and a positive FDG-PET at follow-up: If the positive FDG-PET at follow-up corresponds to a new site of disease confirmed by CT, this is PD. If the positive FDG-PET at follow-up is not confirmed as a new site of disease on CT, additional follow-up CT scans are needed to determine if there is truly progression occurring at that site (if so, the date of PD will be the date of the initial abnormal FDG-PET scan). If the positive FDG-PET at follow-up corresponds to a pre-existing site of disease on CT that is not progressing on the basis of the anatomic images, this is not PD.
- c. FDG-PET may be used to upgrade a response to a CR in a manner similar to a biopsy in cases where a residual radiographic abnormality is thought to represent fibrosis or scarring. The use of FDG-PET in this circumstance should be prospectively described in the protocol and supported by disease-specific medical literature for the indication. However, it must be acknowledged that both approaches may lead to false positive CR due to limitations of FDG-PET and biopsy resolution/sensitivity.

Note: A ‘positive’ FDG-PET scan lesion means one which is FDG avid with an uptake greater than twice that of the surrounding tissue on the attenuation corrected image.

## 12.4 Response Criteria

### Evaluation of Target Lesions

Complete Response (CR): Disappearance of all target lesions. Any pathological lymph nodes (whether target or non-target) must have reduction in short axis to <10 mm.

Partial Response (PR): At least a 30% decrease in the sum of the diameters of target lesions, taking as reference the baseline sum diameters.

Progressive Disease (PD): At least a 20% increase in the sum of the diameters of target lesions, taking as reference the smallest sum on study (this includes the baseline sum if that is the smallest on study). In addition to the relative increase of 20%, the sum must also demonstrate an absolute increase of at least 5 mm. (Note: the appearance of one or more new lesions is also considered progressions).

Stable Disease (SD): Neither sufficient shrinkage to qualify for PR nor sufficient increase to qualify for PD, taking as reference the smallest sum diameters while on study.

### Evaluation of Non-Target Lesions

Complete Response (CR): Disappearance of all non-target lesions and normalization of tumor marker level. All lymph nodes must be non-pathological in size (<10 mm short axis). Note: If CA125 is initially above the upper normal limit, it must normalize for a patient to be considered in complete clinical response.

Non-CR/Non-PD: Persistence of one or more non-target lesion(s) and/or maintenance of CA125 level above the normal limits.

Progressive Disease (PD): Appearance of one or more new lesions and/or unequivocal progression of existing non-target lesions. Unequivocal progression should not normally trump target lesion status. It must be representative of overall disease status change, not a single lesion increase

Although a clear progression of “non-target” lesions only is exceptional, the opinion of the treating physician should prevail in such circumstances, and the progression status should be confirmed at a later time by the review panel (or Principal Investigator).

### Progression Based on Serum CA-125 (for randomized phase 3 trials of initial therapy of ovarian, fallopian tube and primary peritoneal cancer ONLY):

Progression can be based upon serum CA-125, only during the period following completion of cytotoxic chemotherapy, if one of the three conditions is met:

1. Patients with elevated CA-125 pretreatment and normalization of CA-125 must show evidence of CA-125 greater than or equal to two times the upper normal limit on two occasions at least one week apart

OR

2. Patients with elevated CA-125 pretreatment, which never normalizes must show evidence of CA-125 greater than or equal to two times the nadir value on two occasions at least one week apart

OR

3. Patients with CA-125 in the normal range pretreatment must show evidence of CA-125 greater than or equal to two times the upper normal limit on two occasions at least one week apart. When disease progression is defined by CA-125 criteria alone, imaging using the same modality and encompassing the same field as in the initial pretreatment evaluation should be obtained within 2 weeks that such progression is documented.

### Evaluation of Best Overall Response

The best overall response is the best response recorded from the start of the treatment until disease progression/recurrence (taking as reference for progressive disease the smallest measurements recorded since the treatment started). The patient's best response assignment will depend on the achievement of both measurement and confirmation criteria.

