### **Concomitant medication and treatment**

Concomitant medication is defined as any prescription or over-the-counter preparation, including vitamins and supplements. Patients may continue their baseline medication(s). All concomitant medication(s) must be recorded. Any diagnostic, therapeutic or surgical procedure performed during the study period should be recorded, including dates, description of the procedure(s) and any clinical findings.

LY3023414 is a weak inhibitor of cytochrome P450 3A4 (CYP3A4) in patients and thereby impacts (decreases) the metabolic clearance of drugs that are metabolized through CYP3A4 (See also IB Section 6.1.2). The clinical implications of this risk have yet to be determined. Patients should avoid taking concomitant medications that are CYP3A4 substrates (for example, midazolam).

Investigators should monitor patients for unexpected clinical adverse effects as a result of unexpected high exposure to LY3023414 due to any potential interaction of concomitant medications with LY3023414.

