## 11.1 TOXICITIES/SIDE EFFECTS

The dose delay and reduction instructions provided in Tables 11A and 11B are intended to serve as guidelines to allow ongoing treatment for patients experiencing clinical benefit without signs or symptoms of progression while ensuring patient safety. Patients may temporarily suspend dosing of LY3023414 for up to 14 days if they experience toxicity that is considered related to LY3023414 and requires that a dose be held. Patients who miss ≥ 14 consecutive days of scheduled LY3023414 treatment because of LY3023414 related AEs will be discontinued from the study. LY3023414 dosing delay beyond 2 weeks and up to 28 days may be permissible, if AEs are not considered to be primarily related to LY3023414 and the investigator deems continuation to have clinical benefit for the patient. Exceptions may be made after discussion with the approval by the Principal Investigator. Patients may suspend dosing of study drug for radiation therapy or surgery that is considered by the treating physicians to be of clinical benefit for the patient. After completion of the intervention, patients may restart the study drug as long as all criteria for dosing are met and there is no evidence of disease progression (unless approved by PI and sponsor as noted previously).

Dose modifications for LY3023414 for select AEs, should follow the guidance provided in Table 11A, and required dose reductions should follow the dose levels outlined in Table 11B. No dose re-escalation will be allowed.

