#### **14.1 BIOSTATISTICS**

This study aims to assess the activity of LY3023414 in patients with PI3K-pathway activated recurrent or persistent endometrial cancer as measured by the best overall response rate as determined by RECIST 1.1. Assuming we use a binary endpoint of response, defined as best overall response of CR or PR versus not, a sample size of 25 patients provides 90% power to test the hypothesis that the response rate is promising (defined as 30% or higher) against a non-promising rate of 10% or lower. This calculation is based on historical data from studies with ineffective agents in a similar patient population, which have ORR < 10% and PFS rate at 6 months < 20% (Fracasso et al, 2006, Schilder et al. 2004, Garcia et al. 2008 Aghajanian et al, 2011), and uses an exact, one-sample test for binomial proportion, with Type I error=10%. At the end of the study, if at least 5/25 responses are observed then this will be considered a positive study (i.e. conclude that RR is >10%).

Based on historical accrual rates in similar populations, and with the increased prior lines of therapy that will not be allowed for eligibility, we anticipate successful enrollment of 2 patients per month yielding a total accrual time of 12 months. Accrual will continue until 25 evaluable for response patients are treated (evaluable patients are defined in section 12.1)

In addition we will report the following statistics:

1. The clinical benefit rate (CBR) of LY3023414 therapy, defined as the percentage of patients with complete response (CR) + partial response (PR) + stable disease (SD)  $\geq 12$

- weeks from the start of treatment will be reported and the 90% confidence interval will be estimated using exact binomial proportions
2. Progression free survival (PFS), defined as the duration of time from start of treatment to time of recurrence, progression, or death due to any cause, whichever occurs first. Patients will be censored at last follow up date. The Kaplan Meier estimate of median PFS will be reported.
  3. Overall survival (OS), defined as the duration of time from start of treatment until the date of death due to any cause. Patients will be censored at last follow up date. The Kaplan Meier estimate of median OS will be reported.

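### Tumour shrinkage from permitted on-study radiation or surgery can be scored as a response to LY3023414, because best overall response has no cut-off at local treatment

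*Combined protocol and SAP*

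**What the plan says.** Section 11.1 states: "Patients may suspend dosing of study drug for radiation therapy or surgery", where the treating physicians judge it beneficial. The drug may be restarted afterwards if the dosing criteria are met and there is no progression, with an exception open to the PI and sponsor. Such a patient stays on study and continues to be scanned.

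Section 12.4 sets the window for the endpoint: "The best overall response is the best response recorded from the start of the treatment until disease progression/recurrence". It defines CR and PR by lesion size alone. PR is a fall of at least 30% from the baseline sum of target diameters. Its table asks for confirmation at 4 weeks or more when all target lesions have disappeared. An ordinary PR needs only one documentation at least 4 weeks from baseline.

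Section 14.1 analyses response "defined as best overall response of CR or PR versus not". Its decision rule is that "if at least 5/25 responses are observed then this will be considered a positive study". PFS, OS and DOR are censored at last follow-up, with no provision for intervening local treatment.

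**The concern.** Nothing in the endpoint definition or the analysis separates shrinkage caused by the drug from shrinkage caused by a radiotherapy field or a resection. A lesion irradiated or removed while the patient is on study lowers the target sum, and the next scan can then read PR or CR. The same scans can supply the stable disease of 12 weeks or more that counts toward the clinical benefit rate.

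The trial has one arm, no control and a cut-off of five responders, so one misattributed response can decide the result. With no rule written in advance, such a patient would be scored after her scans are known.

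**Working it through.** **1. Is the route open?** A target lesion that makes up at least 30% of the baseline sum, once removed, meets the PR size criterion provided the other target lesions do not grow. The 4-week conditions do not screen this out, because the effect of resection persists. Three other texts come near the problem but do not settle it:

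- Section 10.0, footnote 4, stops imaging at alternative anti-cancer therapy, but only for patients who discontinued for reasons other than progression.
- Section 6.2, criterion 15, excludes patients in whom major surgery is anticipated. It does not cover surgery that becomes needed later, or radiation.
- Section 16.1 describes independent response review as an institutional process and gives no rule for locally treated lesions.

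**2. The plan's own figures.** Inputs from section 14.1: n = 25, cut-off 5, null rate 10%, target rate 30%, exact one-sample binomial test, type I error 10%, power 90%. With X the number of responders:

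- Type I error: P(X ≥ 5 | 25, 0.10) = 0.0980.
- Power: P(X ≥ 5 | 25, 0.30) = 0.9095.

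Both reproduce. The margin below 10% is only 0.2 percentage points.

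**3. Effect of misattributed responses.** Let c be the share of drug non-responders scored CR or PR because of local treatment. The scored response rate is then p = p0 + (1 − p0) × c, and the type I error is P(X ≥ 5 | 25, p). The documents give no value for c, so the values below are assumptions.

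| True null p0 | c | p | P(X ≥ 5) |
|---|---|---|---|
| 10% | 0 | 0.100 | 0.098 |
| 10% | 0.5% | 0.1045 | 0.113 |
| 10% | 1% | 0.109 | 0.129 |
| 10% | 2% | 0.118 | 0.165 |
| 10% | 4% | 0.136 | 0.247 |
| 8% | 2% | 0.0984 | 0.093 |
| 8% | 4% | 0.1168 | 0.160 |
| 5% | 4% | 0.088 | 0.063 |
| 5% | 8% | 0.126 | 0.200 |

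At the 10% null the error passes 0.10 once p exceeds 0.1006, that is c = 0.0006/0.9, or about 0.07%.

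**4. A fixed number of conversions.** If exactly one of the 25 is certain to be scored a responder through local treatment and the other 24 respond at 10%, the probability of a positive trial is P(X ≥ 4 | 24, 0.10) = 0.214. With two such patients it is P(X ≥ 3 | 23, 0.10) = 0.408. Both are conditional on those patients existing.

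**The case against.** The strongest reply is that the route is narrow. The patient must have neither responded nor progressed. The treated site must be a target lesion carrying a large part of a sum that may span five lesions. There must be no new lesion and no non-target progression. Section 12.2 classes bone lesions as non-measurable, so irradiating bone cannot lower the sum. The surgery in section 11.1 need not be tumour surgery, and section 13.1 lists a treatment delay of more than 28 days among reasons for discontinuation. All of this stands. It makes the event uncommon, but it does not say how to score it.

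The second reply is that section 12.2 already deals with radiation: a lesion in a previously irradiated area is not measurable unless progression is documented or a biopsy at least 90 days later confirms persistence. Because target lesions must be measurable, a reader could fairly apply this to a lesion irradiated on study. That softens the radiation half. It still does not say whether the patient is then a non-responder, non-evaluable or assessed on the remaining lesions, and resection is untouched.

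The third reply is that the null is 10% or lower and section 14.1 cites historical response rates below 10%. This also stands: at a true rate of 5%, even one certain conversion gives P(X ≥ 4 | 24, 0.05) = 0.030.

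**Conclusion.** The gap is real: followed as written, the plan can credit shrinkage from local treatment to LY3023414. The bias in the response rate and the clinical benefit rate is upward. Its size depends on a conversion rate that the documents do not give. At the 10% boundary, where the design controls its error, almost any conversion takes the type I error above 10%, to 0.129 at 1% and 0.247 at 4%. At a true null of 5% with 4% converted it stays at 0.063.

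Three stronger readings are not supported:

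- A reader might infer that the trial's type I error is 21% or 41%. Those figures take one or two conversions as certain, and nothing in the documents says they will occur.
- A reader might infer that the sample size is wrong. It reproduces. The weakness lies in the endpoint rule.
- A reader might infer that every endpoint is flattered. For PFS and DOR the effect can go either way: treating a growing lesion can delay progression, but section 12.4 judges progression against the smallest sum on study, so a sum lowered by local treatment can bring progression forward.

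**What to change.** In sections 12.4 and 14.1, state that:

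- best overall response, and stable disease of 12 weeks or more for the clinical benefit rate, use only assessments made before any on-study radiation or surgery to tumour;
- the best response already achieved before the procedure is kept;
- a patient with no CR or PR before the procedure stays among the 25 as a non-responder and is not replaced, including one treated locally before her first re-scan. This needs saying because section 14.1 accrues until 25 evaluable patients are treated.

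Report PFS and DOR as planned, with a sensitivity analysis censoring at the last tumour assessment before the procedure. That censoring may be informative, so it should not replace the main analysis.

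The data cost is one derived flag, since section 9.2 already requires that "Any diagnostic, therapeutic or surgical procedure performed during the study period should be recorded", with dates. The statistical cost is a slightly lower observed response rate and the loss of any later true response in these patients, including one in untreated lesions. If one or two of the 25 become forced non-responders, worst-case power is P(X ≥ 5 | 24, 0.30) = 0.889 or P(X ≥ 5 | 23, 0.30) = 0.864, against 0.910. The type I error at the 10% null is then 0.085 or 0.073. These power figures assume that none of the affected patients had responded before the procedure. The change concerns scoring only and leaves the permission for local treatment as it is.
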